7.3.6 Safety analysis

All randomized patients receiving at least a treatment dose will be included in the safety analysis.

Adverse events will be coded using the last updated version of the Medical Dictionary for Regulatory Activities (MedDRA) dictionary to give a preferred term (PT) and a system/organ class term (SOC) for each event. The number of patients who experienced at least one AE, study product-related AE, serious AE, severe AE and the number of patients withdrawn due to AE will be summarized by treatment arm.

For each SOC and preferred term, summaries will be made with respect to the proportion of patients having at least one occurrence of that event during the trial and the total number of events. The incidence of AEs in each treatment arm will be presented overall, by SOC and preferred term, and additional grouping by severity and relationship to the trial treatment. The comparisons will be analyzed using chi-square test.

Physical Examination data will be listed only, excepting baseline data, which will be summarized in terms of proportion of normal/abnormal findings.

7.4 Planned Interim Analysis(es)

No interim analysis is planned.

8. Data management

During each study visit, the study Investigator (or designee) will collect and report study data in the relevant patient's chart, documenting all significant observations.

Any contact with the patient via telephone or other means that provides significant clinical information shall be documented in the source data.

An Electronic Case Report Form (e-CRF) will be used to record patient's study data.

The Investigator will maintain a list of all persons authorized to make entries and/or corrections on the CRFs. Each authorized person will be provided with a user-specific ID protected by a renewable password. Data entries and corrections will be made only by the authorized persons. The e-CRF system will record date and time of any entry and /or correction and the user ID of the person making the entry/correction. The system will keep track of all old and new values (audit trail). It is the responsibility of the Investigator to ensure that the CRFs are properly and completely filled in. The CRFs must be completed for all subjects who have been included in the study. The Investigator will review all CRFs and electronically sign and date them for each subject, verifying that the information is complete, true and correct. All fields on the CRF must be completed as applicable.

Subjects will be provided with paper questionnaires. Such documents will be filled by the subjects during the study visits, to record data concerning their skin condition.

It is responsibility of the Investigators to instruct the study participants on how to fill in questionnaires in a clear way and preferably in black ball-point pen. The questionnaires will be anonymous, each subject is identified through the subject screening number. A copy of all questionnaires will be stored in patient's chart. It is responsibility of the Investigators to correctly enter the data collected on the questionnaires in the relevant sections of the e-CRF. Questionnaires will be considered source data.

Checks to assist during the data entry and to assess the appropriateness and consistency of data will be developed on the e-CRF system. E-CRF pages will be reviewed both on site by the monitor of the center and remotely, by the data management staff of the CRO. Data Clarification Forms (DCF) will be generated through the e-CRF system, both automatically, through edit checks, and manually, by CRAs and/or data

managers, and the Investigator will have to check and solve them. Occasionally, paper DCF can be sent to the site for resolution. The Investigator is responsible for the review and approval of all query resolutions.

9. Amendments to the CIP

Changes to the clinical investigation plan may only be made by means of a written amendment, which has to be approved and signed by the authorized representatives of the Sponsor, and by the Investigator. Exhaustive justifications that motivate the amendment to the clinical investigation plan should clearly be addressed in the document.

All substantial Clinical Investigation Plan amendments must be submitted to IEC and to Regulatory Authority (if applicable) for review and approval unless it covers administrative issues only. In this case the IEC and the Regulatory Authority (when applicable) will be notified of the amendment without the request to review and approve it.

The Investigator, the Sponsor and IEC, separately or together, should decide whether the subject's informed consent form needs to be changed.

10. Deviations from clinical investigation plan

The Investigator is to conduct the study in accordance with the relevant, current clinical investigation plan and will only deviate when necessary to protect the safety, rights and welfare of the subjects. In the event that an isolated, unforeseen instance occurs resulting in a clinical investigation plan deviation, the Investigator is to document this deviation and notify the CRO as soon as possible. In no instance should this increase the subject's risk or affect the validity of the study.

11. Device accountability

The Investigator is responsible of ensuring accountability of the study product, including reconciliation of study product and maintenance of records.

Upon receipt of the study product, the Investigator (or designee) will check the contents and acknowledge receipt by signing (or initialing) and dating the documentation provided by the Sponsor and returning it to the Sponsor. A copy will be retained in the Investigator File.

The dispensing of the study product will be carefully recorded on the appropriate accountability forms provided by the Sponsor and an accurate accounting will be available for verification by the Study Monitor at each monitoring visit.

Study product accountability records will include:

- ✓ Confirmation of study product receipt at the clinical site.
- ✓ The inventory at the site of study product provided by the Sponsor.
- ✓ The bottles delivery to each subject.
- ✓ The return to the Sponsor or alternative disposition of unused study product.

The Investigator should maintain records that adequately document:

- ✓ That the subjects were provided the doses specified by the Clinical Investigation Plan/amendment(s), and
- ✓ That all study products provided by the Sponsor were fully reconciled.

Unused study product must not be discarded or used for any purpose other than the present study.

Study product that has been dispensed to a subject must not be re-dispensed to a different subject.

The Study Monitor will periodically collect the study product accountability forms and will check all returns (both unused and used containers) before arranging for their return to the Sponsor or authorizing their destruction by the clinical site.

12. Statement of compliance

The study will be conducted in compliance with the current version of the Declaration of Helsinki, with the clinical investigation plan, the ISO 14155:2012, the Italian laws in force and the principles of the Good Clinical Practice.

The clinical investigation will start at clinical site only after obtaining the approval of the relevant Ethics Committee.

13. Informed consent process

The Investigator is responsible for and will obtain informed consent from each subject in the study, in accordance with the ICH-GCP Guidelines, and the current version of the Declaration of Helsinki.

All subjects invited to participate in the study are entitled to make their voluntary decision based on all current available information provided to them by the Investigator/designee. In addition, they will be given a document in native language written in clear concise lay language for review and consideration. The document will previously have been approved by the relevant independent Ethics Committee (IEC) and may further be updated as new important information becomes available that may affect subject's willingness to participate or continue in the study.

The subject must be made aware that he/she may refuse to join the study or may withdraw his/her consent at any time without prejudicing further medical care and that he/she is covered by the Sponsor's indemnity insurance in the event of a study related injury. Subjects must also know that their personal medical records may be reviewed in confidence by the Sponsor's staff or representatives and by Regulatory Authority and IEC and that personal information will be collected and retained in a confidential database. Consent will always be given in writing after the subject has had adequate time to review the information and ask questions, if need be. The signed form will be reviewed by the study Monitor.

14. Adverse events, adverse device effects and devices deficiencies

14.1 Definitions

Adverse Event (AE)

Any undesirable experience occurring to a subject, whether or not it is considered causally related to the investigational medical device. An AE may be a clinical finding, a clinical laboratory abnormality or a symptomatic complaint which is considered by the Investigator to be outside the normal variation for that parameter.

Adverse Device Effect (ADE)

Any untoward and unintended response to a medical device. This includes any event resulting from insufficiencies or inadequacies in the instructions for use or the deployment of the device and any event that is a result of a user error.

Device Deficiency

Inadequacy of a medical device with respect to its identity, quality, durability, safety or performance (included malfunctions, use errors and inadequate labelling).

Serious Adverse Event (SAE)

A serious adverse event (SAE) could be any event that suggests a significant hazard, contraindication, side effect, or precaution. The seriousness of an AE relates to its clinical significance and its potential impact on health.

An AE will be considered as serious when:

Lead to death

Lead to serious deterioration in the health of the subject, that either results in:

- a. a life-threatening illness or injury, or
- b. a permanent impairment of a body structure or a body function, or
- c. in-patient or prolonged hospitalization, or
- d. medical or surgical intervention to prevent life threatening illness or injury or permanent impairment to a body structure or a body function

Lead to foetal distress, foetal death or a congenital abnormality or birth defect.

Serious Adverse Device Effect (SADE)

Adverse device effect that has resulted in any of the consequences characteristic of a serious adverse event or that might have led to any of these consequences if suitable action had not been taken or intervention had not been made or if circumstances had been less opportune.

Unanticipated Serious Adverse Device Effect (USADE)

Serious adverse device effect which by its nature, incidence, severity or outcome has not been identified in the risk analysis report.

14.2 Adverse Event Intensity/Causality

The Investigator, based on his direct observation or on subjects' report, will record the event according to the current version of CTCAE:

Grade 1 (Mild): asymptomatic or mild symptoms; clinical or diagnostic observations only;

intervention not indicated.

Grade 2 (Moderate): minimal, local or noninvasive intervention indicated; limiting age-appropriate instrumental daily life activities.

Grade 3 (Severe): medically significant but not immediately life-threatening; hospitalization or prolongation of hospitalization indicated; disabling; limiting self -care daily life activities.

Grade 4 (Life-threatening consequences): urgent intervention indicated.

Grade 5: Death related to AE.

The relationship of any AE to the product will be classified by the Investigator as follows:

Description	Definition
Certain	The AE is clearly related to the study product
Probable	The AE is likely related to the study product
Possible	The AE may be related to the study product
Unlikely	The AE is unlikely related to the study product
None	The AE is clearly not related to the study product
Unknown	Causality is not assessable, for one reason or another, e.g. because of insufficient evidence, conflicting data or poor documentation

14.3 Adverse Event, Device Deficiency, Adverse Device Effect reporting

The investigator will report to the Sponsor any AEs, Device Deficiencies and ADEs concerning the medical device occurring during the study. He/She will also co-operate with the Sponsor in connection with the reporting of any SADE to the Competent Authority and to the Independent EC, if applicable.

All AEs regardless of severity occurring between recruitment and completion of the study by a subject must be recorded on the AE form provided with the CRF.

If there is a significant worsening of a medical condition that was present before starting the study, this should be considered as a new AE and a complete evaluation recorded.

Signs and symptoms considered as lack of efficacy and occurring during the study will not be recorded on the AEs Section of the CRF except on the condition that, in the Investigator's opinion, these signs and symptoms are caused by any reason different from lack of efficacy of the study product or meet the definition of serious AE.

In the event of a SADE/SAE the Investigator has to:

- Complete the relevant CRF pages and a reporting form with the all available initial information,
- Immediately inform the CRO by telephone,
- Fax the completed report form to the contact person at the CRO or to the Sponsor as soon as possible.

SAE/SADE reporting contacts are on page 4 of this Clinical Investigation Plan.

The Investigator is responsible for ensuring the follow-up of any subject who experiences an SAE/SADE during the study. The investigator must re-examine the subject at regular intervals until the symptoms have completely disappeared or stabilized.

15. Vulnerable population

This section is not applicable, since no subject belonging to any vulnerable population will be recruited for participating in this study.

16. Suspension or premature termination of the clinical investigation

Unless premature interruption occurs, the end of the study will be the closure visit at the clinical site.

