2. Identification and description of the investigational device

Xonrid® is an EC-marked medical device class IIa for radiation dermatitis; it is a topical gel that prevents and treats skin symptoms such as erythema, itching, burning sensation and pruritus, induced by radiotherapy or other causes.

When applied to the target skin areas, Xonrid® forms a protective film, reduces the TEWL (Trans Epidermal Water Loss) and increases moisturizing.

It promotes the healing process by restoring the physiological hydration levels of the affected skin areas. It can be applied to the target areas including skin folds and creases, with or without minor trauma or abrasions.

Xonrid® is manufactured by Helsinn Healthcare SA.

3. Justification for the design of the clinical investigation

Acute radiation dermatitis is a common side effect of radiotherapy in many forms of cancer, first of all breast and head & neck. The intensity of the reaction depends on radiotherapy parameters (dose per fraction, total dose, use of bolus or other beam-modifying devices, type and energy of radiation, size of the treatment field and site treated) and on concomitant chemotherapy employment. Although with a lesser grade, other factors involved in determining the intensity of radiation dermatitis are comorbidities (e.g. diabetes) and individual susceptibility¹⁻².

Skin reactions during radiotherapy, scored according to different systems, usually span in severity from mild erythema (grade 1) to moist desquamation confined to skin folds (grade 2) or not (grade 3).

Large ulcerations that require surgical procedures (grade 4) with potential lethal consequences (grade 5) are exceptional and should be considered non-acceptable complications in routine practice.

Early onset of severe acute skin reaction during treatment could be responsible for a reduced compliance to the planned schedule of irradiation, so jeopardizing local disease control.

The most used scales for assessing toxicities (Radiation Therapy Oncology Group RTOG and CTCAE) do not capture symptoms as reported by the patients. Moreover, adverse events assessed by physicians are less accurate than patient-reported outcome (PRO) instruments and some clinicians have proposed replacing physician scales with patient-assessed reporting of adverse events³⁻⁴.

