6.2 Investigational device and comparator

6.2.1 Xonrid®

The product under investigation is Xonrid®.

Name: Xonrid®

Formulation: Gel

Route of administration: Topical

Composition: the composition of Xonrid®, including ingredient function, as reported in the commercial available product, is reported in Table 4.

Xonrid® is a short term use, Class IIa Medical Device, a topical gel designed for RT-induced dermatitis. When applied to the target skin areas, Xonrid® forms a protective film, reduces the trans-epidermal water loss (TEWL) effect induced by external factors and increases moisturizing. The component responsible for the formation of this film is mainly Hyaluronic Acid, that also helps to achieve an optimal moisturizing effect. The other components responsible for the formation of this film are: polyacrylamide gluconolactone, and Xanthan gum. In particular, gluconolactone is a polyhydroxy acid, with a strong hygroscopic moisturizing power, as well as a glycerin effect. Moreover, the device includes sweet almond oil, known for its emollient, softening, nourishing and soothing properties, and is particularly effective in the treatment of dry, reddened and sensitive skin areas. It promotes the healing process by restoring the physiological hydration levels of the affected skin areas. It can be applied to the target areas including skin folds and creases, either presenting or not minor traumas or abrasions. On these bases, Xonrid® may represent a promising device for the prevention of radiation dermatitis.

Table 4: Xonrid® ingredients with relative function

Ingredient	Function
Glycerin (Glycerol)	Humectant
Gluconolactone, sodium benzoate, calcium gluconate	Preservative
Chamomilla recutita water	Masking agent
Xanthan gum	Rheology additive
C12-15 alkyl benzoate	Emollient
Ethylhexyl palmitate	Emollient
Disodium EDTA	Chelanting agent
Glyceryl stearate	Emollient
Prunus amygdalus dulcis oil	Emollient
Polyacrylamide, C13-14 isoparaffin, laureth-7	Viscosity increasing agent
Vitis vinifera extract, aqua, propylene glycol	Skin conditioning agent
Aqua	Solvent
Sodium hyaluronate	Skin conditioning agent
Propylene glycol, aqua, camelia sinensis extract	Skin conditioning agents
Propylene glycol, hydrolyzed RNA, hydrolyzed DNA	Skin conditioning agents

Raspberry ketone	Skin conditioning agent
Propylene glycol	Solvent
Tocopheryl acetate	Preservative/ Antioxidant agent

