6.2.1.1 Packaging and labelling

Xonrid® will be manufactured and provided for the study by Helsinn Healthcare SA, the Sponsor of this clinical investigation.

The study product shipment to the study site will be done only after the completion of all Ethics and Administrative procedures.

The product will be labeled as experimental treatment in accordance with Good Manufacturing Practice (GMP, Annex 13).

The primary package is a bottle containing 75 ml of gel. Subjects randomized to Xonrid® + SOC will receive a total of:

1. no. 12 bottles if head & neck cancer subjects
2. no. 4 bottles if breast cancer subjects.

The number of bottles assigned should be enough for the whole study duration (56 ± 2 days / 63 ± 2 days).

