## 12. SAFETY EVALUATION

### 12.1 Extent of Exposure

### 12.2 Adverse Events

Adverse events will be coded according to MedDRA, version 21.1. AEs will be summarized by treatment arm in terms of the number of patients who experienced at least one AE, study product-related AE, serious AE, severe AE and the number of patients withdrawn due to AE will be summarized. The comparisons will be analyzed using chi-square test. For each SOC and preferred term, summaries will be made with respect to the proportion of patients having at least one occurrence of that event during the trial and the total number of events.

```
proc freq;
table treatment * cat_variable / CHISQ;
run;
```

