### 12.3 Other safety endpoints

Tolerability assessment will be based on the evaluation of site administration adverse events.

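### The lack-of-efficacy exception to AE recording is undefined for Group B, so skin AEs may be recorded differently by arm, in Xonrid's favour, and gel irritation may be under-counted

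*Protocol*

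**What the plan says.** Protocol 14.3 sets a general duty: "All AEs regardless of severity occurring between recruitment and completion of the study by a subject must be recorded on the AE form". Later in the same section it takes some events out: "Signs and symptoms considered as lack of efficacy and occurring during the study will not be recorded on the AEs Section of the CRF". That exception has its own limit. The event goes back on the form if the investigator takes the view that "these signs and symptoms are caused by any reason different from lack of efficacy of the study product or meet the definition of serious AE".

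Protocol 6.2.1 identifies the study product: "The product under investigation is Xonrid". Protocol 6.2.1.1 gives the bottle supply under "Subjects randomized to Xonrid® + SOC will receive a total of", so only Group A has it. Group B follows the standard-of-care measures, with no gel and no vehicle (Protocol 6.1 and 6.2.2). The study is open label. Neither document says how the exception applies to Group B.

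Protocol section 2 describes the gel as one that "prevents and treats skin symptoms such as erythema, itching, burning sensation and pruritus, induced by radiotherapy or other causes".

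On analysis, SAP 12.2 says of the AE summaries by arm: "The comparisons will be analyzed using chi-square test". SAP 12.3 says: "Tolerability assessment will be based on the evaluation of site administration adverse events". SAP 9.1 has each cancer site analysed separately.

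**The concern.** The symptoms that the gel is meant to relieve are also those that a local reaction to it would produce, in the same area of skin. The protocol makes the investigator's view of the cause a condition for recording, gives no criteria for that view, and leaves it to someone who knows the allocation.

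Two things are at stake.

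- **The comparison between arms.** Taken literally, a skin sign in Group B cannot be lack of efficacy of a product that the patient never received, so it is recordable. The same sign in Group A may be left off. A lower AE count under Xonrid could then come from the recording rule alone.
- **Tolerability.** This is an objective in Protocol 5.3. A gel reaction put down to ordinary dermatitis does not reach the AE form, and SAP 12.3 names no other source.

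**Working it through.** **The plan's own figure.** The plan states 18 patients per group for 38.2% against 82.9%, two-sided 0.05, 80% power. The mean proportion is (0.382 + 0.829)/2 = 0.6055.

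n = [1.960 × √(2 × 0.6055 × 0.3945) + 0.842 × √(0.382 × 0.618 + 0.829 × 0.171)]² / 0.447² = (1.355 + 0.517)² / 0.1998 ≈ 17.5, so 18. Power at 18 is 81.1%.

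With 10% dropout, 18/0.9 = 20 per arm per site. The figure reproduces. It does not bear on the AE rule, but it supplies the 20 v 20 used below.

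**Inputs for the illustration**

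- 20 per arm: Protocol 7.1, 1:1 allocation in Protocol 6.4.1, sites analysed separately in SAP 9.1.
- Share with G2 or worse by week 5: 1 − 0.382 = 0.618, the plan's control rate, used in both arms so that there is no true difference.
- s, the share of Group A cases that reach the AE form, with Group B recording all of its cases: assumed at 1, 0.75 and 0.5.
- b, the share of patients with some other AE: assumed at 0, 50% and 80%, independent of dermatitis and equal in both arms.

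**Formulas.** The proportion with at least one recorded AE is

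- Group B: 1 − (1 − b)(1 − 0.618)
- Group A: 1 − (1 − b)(1 − 0.618 s)

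For example, with b = 0.5 and s = 0.5, Group B is 1 − 0.5 × 0.382 = 0.809 and Group A is 1 − 0.5 × 0.691 = 0.654.

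The rejection rate is the summed probability, over all pairs of binomial counts (20 and 20), of those pairs for which the uncorrected chi-square is significant at 0.05.

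| Other AE (b) | Group B | Group A at s = 1 / 0.75 / 0.5 | Test rejects at s = 1 / 0.75 / 0.5 |
|---|---|---|---|
| 0% | 61.8% | 61.8 / 46.4 / 30.9% | 5 / 15 / 48% |
| 50% | 80.9% | 80.9 / 73.2 / 65.4% | 5 / 9 / 20% |
| 80% | 92.4% | 92.4 / 89.3 / 86.2% | 3 / 5 / 8% |

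Where recording differs, most rejections favour Xonrid: 14.8 of 14.9 percentage points at b = 0 and s = 0.75, and 3.8 of 4.5 at b = 80% and s = 0.75.

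The b = 0 row also shows what happens to a comparison of field skin AEs alone. The lower rows are closer to the count of patients with any AE.

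**The case against.** Several points on the other side are sound.

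- **The exception keeps recognised gel reactions.** Irritation that the investigator attributes to the gel has a cause other than lack of efficacy, so it is recordable. Serious events always are. Protocol 14.3 also asks for adverse device effects to be reported, and Protocol 14.2 has a relatedness scale with a possible and an unknown category. Only misattributed reactions are lost.
- **The opening words name no product or arm.** A site could leave dermatitis off the AE form in both arms as an efficacy outcome. It could also treat radiotherapy as the cause and record it in both. Neither practice biases the comparison.
- **Skin data are collected elsewhere.** The skin grade, Skindex-16, spectrophotometry and TEWL are taken weekly in both arms (Protocol 6.4.2 to 6.4.4).
- **A general duty followed by a stated exception is not a contradiction.**

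A reader might infer that local tolerability cannot be assessed at all, or that the AE comparison is certainly biased. The documents support neither. Tolerability is likely under-counted in its planned source. Bias arises only if sites apply the exception to Group A more than to Group B.

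A reader might also extend the bias to severe AEs and withdrawals due to AEs. That is not shown: Protocol 16.1 lists skin toxicity of grade 3 or more as a reason for discontinuation separate from an AE, and no calculation here covers those counts.

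What remains is that the rule is undefined for one arm, an unblinded investigator resolves it case by case, and the SAP does not correct for that. The weekly skin data would help, but the SAP does not assign them to tolerability.

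**Conclusion.** The point holds as a cheap improvement, below must-fix. Recording of field skin signs is open to a difference between arms that would favour Xonrid.

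The size depends on site practice. If Group A records three quarters or half of its cases, false rejection is about 15% or 48% with no other AEs, about 9% or 20% if half of patients have another AE, and about 5% or 8% (against 3% with equal recording) if 80% do. The recording shares and the rate of other AEs are assumptions, since the documents give neither. The 61.8% is the plan's control rate for G2 or worse; milder signs could also be recorded or omitted.

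The primary endpoint rests on the physicians' grade, not on the AE form, and is untouched. Safety and tolerability is among the secondary endpoints, which the plan calls exploratory.

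**What to change.** **Protocol 14.3.** State one recording rule for skin signs in the irradiated or application area that is the same in both arms whatever the supposed cause, and tabulate these events apart from other AEs.

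**SAP.** The SAP describes enrolment as complete, so a new recording rule cannot restore entries never made. The analysis-side changes matter most:

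- SAP 12.2: limit the between-arm AE tests to non-skin AEs, and list field skin AEs descriptively by arm with a note on the recording rule.
- SAP 12.3: supplement the application-site AEs with the weekly CTCAE skin grade and the Skindex items on itch, burning, pain and irritation (items 1 to 4 in Protocol Appendix 3), which are collected identically in both arms.

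**Cost.** A few sentences and one extra table; no new data. The drawback is that the skin measures overlap with the efficacy data, so the text should say that they are shown again as local tolerability and are not independent evidence.
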